
twice a week, together with standard dose lenalidomide and low dose dexamethasone in relapsed or refractory myeloma patients in a phase I/II study with 10 additional patients enrolled at the highest tolerated low azacitidine dose to obtain an initial impression of efficacy and to evaluate whether this dose exerts the expected pharmacodynamic effects in myeloma cells before a larger phase II trial may be conducted. In light of new data supporting use of standard-dose azacitidine in myeloid neoplasia patients with kidney dysfunction(14) and GFR-adjusted lenalidomide for myeloma patients(15), amendment 7 extends the safety and preliminary efficacy evaluations to myeloma patients with GFR 30-59 ml/min (Cockroft-Gault). Lenalidomide will be used at a fixed dose of 10mg daily from day 1-21 every 28 days which yielded equal AUC concentrations in myeloma patients with GFR 30-49m/min as 25mg daily from day 1-21 every 28 days in patients with GFR \geq 80 ml/min in a recent study(15). Only two dose levels of azacitidine will be tested. Dose level "CKD 1" will use azacitidine at 40 mg/m² s.c. twice a week which has been found tolerable in patients with GFR \geq 60 ml/min; one of six patients developed a dose limiting toxicity, culture negative neutropenic fever at an absolute neutrophil count (ANC) nadir of 0.48K/mm³, with resolution the next day at an ANC of 0.89K/mm³ without G-CSF use. At the time of amendment 7, two patients with normal kidney function have completed the first cycle at dose level 5 (azacitidine 50mg/m² s.c. twice a week) without dose limiting toxicities. Six patients with GFR 30-59 ml/min will be treated at CKD 1 if dose limiting toxicities (DLTs) do not occur in more than one patient. If 2 of 3 or 2 of up to six patients develop DLTs at CKD1, subsequent patients will be treated at "CKD -1" (30mg/m² s.c. twice a week). Otherwise (no more than one patient with DLTs at CKD1), subsequent patients will receive azacitidine at 50mg/m² s.c. twice a week (= dose level CKD2). Lower or higher dose levels will not be tested. This modified dose escalation scheme increases safety by enrolling at least 6 patients per dose level and guarantees that the tolerability of twice a week azacitidine in patients with GFR 30-59 ml/min will be defined by enrolling maximally 12 additional patients. Omission of weekly azacitidine is based on the observation that clinical benefit response rates were more than twice as high with twice a week than with weekly azacitidine dosing (40% versus less than 15%) in patients with GFR > 60ml/min, an encouraging result taking into consideration that patients had received a median of 4.5 prior regimens, with myeloma refractory to previous lenalidomide in 88%, to previous proteasome inhibitors in 81%, and to both lenalidomide and proteasome inhibitors in 75%. Once the highest tolerated low dose for patients with reduced GFR (HTLD-CKD) has been defined, enrollment at this dose level may contribute to the 10 patient phase II extension. Before amendment 7 eighteen patients have started treatment, including two at dose level 5. Assuming up to 6 patients will be enrolled per dose level; the maximal number of enrolled patients will therefore increase from previously estimated 40 to 44 after amendment 7.

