The metabolic profile of lenalidomide in humans has not been studied. In healthy volunteers, approximately two-thirds of lenalidomide is eliminated unchanged through urinary excretion. The process exceeds the glomerular filtration rate and therefore is partially or entirely active. Half-life of elimination is approximately 3 hours. Renal impairment increases the area under the curve (AUC) and increases half-life to 9-10 hours with moderate to severe renal dysfunction and to more than 15hours in ESRD making dose adjustments necessary(52). A study presented at ASH 2011 determined lenalidomide AUC concentrations in 37 multiple myeloma patients with various glomerular filtration rates (Cockroft-Gault) who were treated with lenalidomide dosing schedules predicted to yield equal AUCs based on pharmacokinetic data obtained in patients without cancer diagnosis but with chronic kidney disease (CKD)(15). Ten

myeloma patients with GFR > 80ml/min were treated with standard lenalidomide 25mg day 1-21 every 28 days and served as comparison for patients with GFR 50-80 ml/min (n=10), GFR 30-49 ml/min (n=7), GFR < 30 ml/min (n=5), and patients on chronic hemodialysis (n=5), who received 25mg daily, 10mg daily, 15mg every other day, and 5mg daily, respectively, from day 1-21 every 28 days. All patients received dexamethasone 40mg once a week but no other antimyeloma drugs. Average daily AUC values of patients with CKD were between 103-149% of the ones in patients with GFR > 80 ml/min and essentially identical for patients with GFR 30-49 (103%). The renal function remained stable in all patients. Severe adverse events occurred in 60% of patients on dialysis and 45% of remaining patients (p=0.3), overall comparable to reported results(11, 26), as were response rates of around 70% in these patients who had received a minimum of one prior myeloma regimen. In summary, GFR-adjusted lenalidomide dosing achieved appropriate drug exposure and was safe and effective(15).

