5.2.1 Inclusion Criteria

Subjects must meet the following inclusion/exclusion criteria to be eligible for the study.

Inclusion Criteria

1. Understand and voluntarily sign an informed consent form.
2. Age ≥ 18 years at the time of signing the informed consent form.
3. Able to adhere to the study visit schedule and other protocol requirements.
4. Refractory or relapsed multiple myeloma (see under 5.3.)
5. Measurable disease defined as at least one of the following: Serum m-spike $\geq 1\text{g/dL}$, urine m-spike $\geq 200\text{mg/24hrs}$, serum free light chains $\geq 100\text{mg/L}$ (provided the kappa/lambda ratio is abnormal), or bone marrow plasma cells $\geq 30\%$.
6. Previous therapy with IMiD™ compounds (thalidomide, lenalidomide, pomalidomide), proteasome inhibitors (bortezomib, carfilzomib), and corticosteroids must be discontinued at least 14 days before entry onto this study.
7. Previous cytotoxic chemotherapy (e.g. alkylating chemotherapy, anthracyclines, and vinca alkaloids), radiation therapy to the pelvis, and any experimental therapy other than carfilzomib or pomalidomide must have been discontinued at least 28 days prior to entry onto this study.
8. ECOG performance status of ≤ 2 at study entry (see Appendix II).
9. Laboratory test results within these ranges:
 - Absolute neutrophil count $\geq 1,500 / \text{mm}^3$
 - Platelet count $\geq 75,000/\text{mm}^3$
 - Calculated creatinine clearance (Cockcroft-Gault) $\geq 30\text{ml/min}$.
 - Total bilirubin $\leq 1.5 \times \text{ULN}$
 - Serum glutamic-oxaloacetic transaminase (SGOT) (aspartate aminotransferase [AST]) and serum glutamic-pyruvic transaminase (SGPT) (alanine aminotransferase [ALT]) levels $\leq 2 \times \text{ULN}$
10. All study participants must be registered into the mandatory RevAssist® program, and be willing and able to comply with the requirements of RevAssist®.
11. Females of childbearing potential (FCBP)† must have a negative serum or urine pregnancy test with a sensitivity of at least 50 mIU/mL within 10 – 14 days prior to and again within 24 hours of prescribing lenalidomide (prescriptions must be filled within 7 days) and must either commit to continued abstinence from

† A female of childbearing potential is a sexually mature woman who: 1) has not undergone a hysterectomy or bilateral oophorectomy; or 2) has not been naturally postmenopausal for at least 24 consecutive months (i.e., has had menses at any time in the preceding 24 consecutive months).

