5.3 Definition Relapsed Myeloma and Refractory Myeloma

A recent ASH/FDA panel has recommended to include clinical criteria to define relapsed myeloma and to separately analyze data for the relapsed as opposed to the refractory group of patients (56). In accordance with this consensus statement, International Myeloma Working Group diagnostic criteria (57), and the international uniform response criteria (58) the following definitions will be used:

5.3.1 Refractory Myeloma.

Biochemical or clinical evidence of loss of disease control within 90 days after the last therapy. Any of the following defines refractory myeloma:

1. Progressive disease (see 5.8.1) on prior therapy
2. Best response to prior therapy was stable disease (see under 7)
3. Progressive disease (see 5.8.1) within 90 days of the last therapy

5.3.2 Relapsed Myeloma.

Not fulfilling criteria for refractory disease and at least one biochemical **and** at least one clinical criterion fulfilled indicating recurrence of disease more than 90 days after the last therapy:

One or more biochemical criteria for recurrent disease:

An increase of 25% from lowest response value in any one or more of the following, verified on two consecutive measurements:

1. Serum M-component (absolute increase must be ≥ 0.5 g/100 ml) *
2. Urine M-component (absolute increase must be ≥ 200 mg per 24 h)
3. Only in patients without measurable serum and urine M-protein levels: the difference between involved and uninvolved FLC levels (absolute increase must be >100 mg/l)
4. Bone marrow plasma cell percentage (absolute % must be $\geq 10\%$)

AND one or more clinical criteria for recurrent disease:

Any of the following:

1. Definite development of new bone lesions or soft tissue plasmacytomas
2. Definite increase in the size of existing bone lesions or soft tissue plasmacytomas. A definite increase is defined as a 50% (and at least 1 cm) increase as measured serially by the sum of the products of the cross-diameters of each measurable lesion
3. Development of hypercalcemia (corrected serum calcium >11.5 mg / 100ml) that can be attributed solely to the plasma cell proliferative disorder
4. Decrease of hemoglobin by at least 2g/dL below the best independent value (without ESA or blood transfusion for at least 28 days) since the end of previous

therapy or new decrease in HgB below 10g/dL or to 2g/dL below the lower limit of normal

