5.7.5 Instructions for Dose Modifications or Interruption During a Cycle

Table 5 outlines instructions for dose reductions of study drugs for specific toxicities. Study drugs may be temporarily or permanently dose reduced using doses outlined in table 1-4 or temporarily discontinued in other situations where their continued administration according to protocol is felt unsafe by the treating physician.

Table 5: Dose Modifications Azacitidine and Lenalidomide

NCI CTC Toxicity Grade	Dose Modification Instructions
Grade 3 neutropenia associated with fever (temperature $\geq 38.5^{\circ}$ C) or Grade 4 neutropenia	
 • Hold (interrupt) lenalidomide and, while on combination, also azacitidine dose. • Follow CBC weekly. • During combination therapy with lenalidomide and azacitidine: 
 ◦ If neutropenia has resolved to \leq grade 2 prior to Day 21 of the current cycle, restart azacitidine at the next lower dose level and continue lenalidomide at the same dose level if the patient's myeloma has not previously been refractory to lenalidomide, otherwise maintain azacitidine dose level and reduce lenalidomide by one dose level (if the patient is only on one of these drugs reduce its dose by one level) and continue treatment through the scheduled end of the cycle. Otherwise, omit treatment for the remainder of the cycle and reduce dose levels in the same way at the start of the next cycle. Omitted doses are not made up. ◦ If neutropenia is the only toxicity for which a dose reduction is required (no fever or other reason to reduce doses), G-CSF should be considered instead of a dose reduction. • During maintenance therapy with lenalidomide: 
 ◦ If neutropenia has resolved to \leq grade 2 prior to Day 21 of the current cycle, restart lenalidomide at the next lower dose level, and continue through the scheduled end of the cycle. Otherwise, omit lenalidomide for the remainder of the cycle and reduce lenalidomide by 1 dose level at the start of the next cycle. Omitted doses are not made up.

Table 5: Dose Modifications Azacitidine and Lenalidomide

NCI CTC Toxicity Grade	Dose Modification Instructions

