10.2.3 Response

The response rate (RR= sCR+CR+VGPR+PR) and clinical benefit response rate (CBRR=sCR+CR+VGPR+MR) will be analyzed for the entire study group, and for the 16-22 patients treated at the HTLD / HTLD-CKD according to whether patients had relapsed or refractory disease at study entry. All response categories require two consecutive assessments but the time a response is first reached will be used to calculate response rates after 6 and 12 cycles. Additionally, best response will be reported. If one or more patients on this trial elect to undergo stem cell transplantation, response before mobilization will be reported.

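### Response is split only by relapsed versus refractory disease, which is not lenalidomide-specific, so responses the lenalidomide-dexamethasone backbone could give alone are not shown separately

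*Combined protocol and SAP*

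**What the plan says.** Section 10.2.3 analyses the response rate (RR) and the clinical benefit response rate (CBRR) for the entire group and for the "16-22 patients treated at the HTLD / HTLD-CKD", divided "according to whether patients had relapsed or refractory disease at study entry". Section 10.3 adds no other response split.

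Section 5.3 gives the reason for the division: a consensus panel advised investigators "to separately analyze data for the relapsed as opposed to the refractory group of patients". The lead sentence of 5.3.1 describes refractory disease as "Biochemical or clinical evidence of loss of disease control within 90 days after the last therapy". Of the three criteria beneath it, items 1 and 2 refer to prior therapy and item 3 to the last therapy. None names a drug. Section 5.3.2 defines relapsed disease as not meeting the refractory criteria, with recurrence more than 90 days after the last therapy.

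The disease criterion for entry (5.2.1) is "Refractory or relapsed multiple myeloma (see under 5.3". The lenalidomide-related exclusions in 5.2.2 concern intolerance, hypersensitivity and a specific skin reaction. They do not exclude lenalidomide-naive or lenalidomide-sensitive disease.

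The protocol does use lenalidomide-refractory status elsewhere. The Synopsis describes the patients treated so far "with myeloma refractory to previous lenalidomide in 88" percent. Table 5 in 5.7.5 makes dose changes depend on it ("if the patient's myeloma has not previously been refractory to lenalidomide"), and so does the re-escalation guidance in 5.7.3.

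**The concern.** The extension is meant to give a first impression of whether adding azacitidine to lenalidomide-dexamethasone helps, before a larger phase II trial. In a single-arm trial on an active backbone, a response in a patient whose myeloma has never been refractory to lenalidomide says less about azacitidine than a response in a patient whose myeloma has.

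The planned split does not follow that distinction. A lenalidomide-naive patient who progressed on bortezomib is classed as refractory. On the last-therapy wording of 5.3.1, a patient who was refractory to lenalidomide some regimens ago, and who recurs more than 90 days after a later drug, could be classed as relapsed. Either stratum can therefore contain both kinds of patient, and the overall rate moves with the share of non-refractory patients who happen to enrol.

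**Working it through.** **The plan's own counts.** One cohort at its highest tolerated low dose plus the extension gives 6 + 10 = 16. Both cohorts give 6 + 6 + 10 = 22. This reproduces the 16-22 in 10.2.3. The total also reproduces: 18 started + 4 more at dose level 5 + 12 with reduced GFR + 10 in the extension = 44.

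**The mix so far.** The Synopsis reports 88% refractory to lenalidomide, 81% to proteasome inhibitors and 75% to both. Among denominators from 5 to 18, only 16 fits all three (14, 13 and 12 patients). The denominator is inferred, not stated. On that basis:

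- not lenalidomide-refractory: 16 − 14 = 2
- proteasome-inhibitor-refractory but not lenalidomide-refractory: 13 − 12 = 1

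That last patient could sit in the refractory stratum while still lenalidomide-sensitive, so the misalignment is not merely theoretical.

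**Response to the backbone without azacitidine.** Section 5.1.1.3 describes lenalidomide with weekly dexamethasone and no other antimyeloma drug as comparable with earlier results, "as were response rates of around 70% in these patients who had received a minimum of one prior myeloma regimen". The Synopsis gives a median of 4.5 prior regimens here, so 70% is probably high. I take 40% as an assumed lower value.

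**Contribution to RR** = (patients not lenalidomide-refractory ÷ n) × backbone response rate.

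| n | Not refractory (12%, rounded) | At 40% | At 70% |
|---|---|---|---|
| 16 | 2 | 0.40 × 2/16 = 5.0 points | 0.70 × 2/16 = 8.8 points |
| 22 | 3 | 0.40 × 3/22 = 5.5 points | 0.70 × 3/22 = 9.5 points |

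Without rounding to whole patients, the figures are 0.12 × 40 = 4.8 and 0.12 × 70 = 8.4 points for either n.

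**Chance of at least one such responder.** For 2 patients: 1 − 0.6² = 64% at 40%, and 1 − 0.3² = 91% at 70%. For 3 patients: 1 − 0.6³ = 78%, and 1 − 0.3³ = 97%.

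**Effect on reading the result.** If the true RR in lenalidomide-refractory patients were 10%, the pooled rate would be 0.88 × 10 + 0.12 × 40 = 13.6% at the lower assumption, and 0.88 × 10 + 0.12 × 70 = 17.2% at the upper.

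**What a lenalidomide split would leave.** About 14 of 16 or 19 of 22 patients stay in the refractory stratum. With no responders there, the exact 95% upper limit would be 23% or 18%. The other stratum is very small: 0 of 2 has an upper limit of 1 − 0.025^(1/2) = 84%.

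**The case against.** Several points on the other side stand.

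- **The existing split has a documented source.** It follows a panel recommendation and is legitimate. The gap is a missing addition, not a wrong analysis.
- **The relapsed example depends on the wording.** Under items 1 and 2 of 5.3.1, read literally, a patient who progressed on earlier lenalidomide is refractory whatever came later. The bortezomib example holds on either reading.
- **A reader might infer that only responses in lenalidomide-refractory patients are informative.** The documents do not support that. The rationale also concerns deeper and longer responses. Other planned or reported evidence bears on azacitidine's role: the correlation of response with cytidine deaminase activity (4.1.2, 5.7.2), the paired methylation and expression studies (5.5), and clinical benefit by schedule in the Synopsis (40% twice weekly against less than 15% weekly). None of these is a control arm.
- **A reader might infer a contribution of 18 to 35 points.** That needs 4 to 8 non-refractory patients among 16 at 70% (0.70 × 4/16 = 17.5; 0.70 × 8/16 = 35). No mix in the documents supports such a share. The clinical benefit rate under 15% with weekly azacitidine on the same backbone also argues against a large backbone effect in the patients enrolled so far, although their mix is not given by schedule.
- **The shift is small beside sampling error.** For 6 responders of 16, the exact 95% interval is 15% to 65%.
- **Response is secondary.** The plan sets no null rate, target rate or go/no-go rule, so no decision in the protocol turns on this split.

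**Conclusion.** The point holds as an omission. The only planned response split is not lenalidomide-specific, lenalidomide-sensitive patients may enrol, and a status the protocol already uses for dose changes and for describing its interim results has no place in the response analysis.

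The size is modest: roughly 5 to 9 points of RR. This rests on the 88% lenalidomide-refractory share reported before amendment 7 and on an assumed backbone response of 40% to 70% in the remaining patients. It would grow only if later enrolment brought in more non-refractory patients. No rule prevents that, and nothing in the documents shows that it will happen.

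A reader might also conclude that the lenalidomide-refractory subset should become the lead efficacy population. The documents do not support that step. The trial was designed for relapsed or refractory disease, and the change would be made after 18 patients had started and interim response rates were known.

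**What to change.** In 10.2.3, add a descriptive table of RR and CBRR with exact 95% intervals by lenalidomide-refractory status, for the patients at the HTLD / HTLD-CKD and for the entire group. Define lenalidomide-refractory in parallel with 5.3.1: progression on, or within 90 days of, a lenalidomide-containing regimen, or stable disease as best response to one. All other patients form the second group.

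State that the overall rate will be read alongside the lenalidomide-refractory rate, and that the table was added after the interim results in the Synopsis were known. Keep the relapsed/refractory split, and keep the overall population as the lead analysis. In the same edit, reconcile the CBRR formula in 10.2.3, which omits PR, with the objective of minor response or better, since the new table depends on it.

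The cost is one more table and a definition. No new patients or procedures are needed, because prior anti-cancer therapies are recorded at screening and sites must already know the status to apply Table 5. The non-refractory stratum will be too small to interpret alone, and attribution to azacitidine remains unresolved.

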10.2.4 Progression-free Survival

Progression-free survival will be calculated from the time of enrollment until the development of progressive disease or death from any cause, whichever occurs first. Patients who elect to undergo high dose chemotherapy followed by autologous stem cell transplantation will not be included in an analysis of progression-free survival.

10.2.5 Overall Survival

Overall survival will be calculated from the time of study entry until the date of death from any cause. Patients who elect to undergo high dose chemotherapy followed by autologous stem cell transplantation will not be included in an analysis of overall survival.

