Physical examination, vital signs, weight	X	X ¹	X	X	X	X		X		X	X	
ECOG performance status	X	X ¹	X	X	X	X		X		X	X	
Skeletal survey ²	X											
Bone marrow ³	X	X ¹				X						
ECG	X											
CBC with differential	X	X ¹	X	X	X	X	X	X	X	X	X	
Research blood sample (10mL EDTA, 10mL Heparin)	X	X	X	X	X	X		X				
Calculated creatinine clearance (by Cockcroft-Gault) ⁴	X	X ¹				X ⁴		X ⁴		X ⁴		
TSH ⁵	X ⁵	X ¹						X ⁵		X ⁵	X ⁵	
SPEP w m-spike, 24hr urine w m-spike, serum and urine immunofixation, serum quantitative immunoglobulins, serum free light chain assay, beta-2 microglobulin,	X	X ¹				X		X		X	X	
Complete metabolic panel	X	X ¹	X	X	X	X	X	X	X	X	X	
LDH, phosphorus, uric acid	X	X ¹										
Pregnancy testing ⁷	X ⁸	X ⁸	X ⁸	X ⁸	X ⁸	X ⁸		X ⁸		X ⁸	X ⁸	
Register patient into RevAssist® program ⁹	X ⁹											
Prescribe lenalidomide via RevAssist® ¹⁰		X ¹⁰				X ¹⁰		X ¹⁰		X ¹⁰		
Azacitidine administration		X ¹¹										
Dexamethasone prescription		X ¹²				X ¹²		X ¹²				
Response assessment ¹³						X		X		X	X	
Record adverse events ¹⁴		X	X	X	X			X		X	X ¹⁴	
Record concomitant therapies/procedures	X	X				X		X		X	X	
Obtain Follow-Up anti-cancer treatments												X
Obtain Follow-Up survival information												X

* Variations of ± 3 days of the scheduled visit are permitted.

If Physical examination, vital signs, weight and ECOG performance status were done within 7 days of Day 1, they do not need to be repeated at Study Day 1. An unscheduled visit can occur at any time during the study. Source must be maintained for these unscheduled visits. The date for the visit and any data generated must be recorded on the appropriate CRF. Source documents for these unscheduled visits must also be maintained.

Version: 07/16/2015

¹ If screening assessments were done within 7 days of Day 1, they do not need to be repeated at Study Day 1.

² A skeletal survey may be obtained up to 28 days before day 1, cycle 1. It will be repeated every 12 months or earlier if symptoms suggest bony progression.

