³ With each bone marrow aspiration two 20mL samples, each containing 2mL of heparin, will be obtained for correlative studies in addition to routine clinical analyses as indicated. In addition to defined times, a bone marrow examination is required to confirm complete response and before high dose melphalan in patients who choose to undergo autologous stem cell transplantation. In patients who have measurable disease only in the bone marrow, the bone marrow biopsy and aspiration will be performed every three cycles (+/- 7 days) while on combination therapy and every six cycles (+/- 7 days) while on maintenance.

⁴ Calculated creatinine clearance (by Cockcroft-Gault) at baseline and before dosing at the start of each cycle until cycle 12, then every two cycles.

⁵ To include Thyroid Stimulating Hormone (TSH) at screening, at least every 16 weeks and at treatment discontinuation. To facilitate monitoring in the maintenance phase it is recommended to obtain TSH at day 1 of cycle 1, 4, 8, 12, 16, and so on. T3 and T4 levels may be assessed as clinically indicated.

⁶ If patients undergo stem cell transplantation before completion of six cycles, SPEP w m-spike, 24hr urine w m-spike, serum and urine immunofixation, and serum free light chain assay should be repeated before mobilization begins for confirmation of their pre-transplant response.

⁷ Pregnancy tests for females of childbearing potential. A female of childbearing potential (FCBP) is a sexually mature female who: 1) has not undergone a hysterectomy or bilateral oophorectomy; or 2) has not been naturally postmenopausal for at least 24 consecutive months (i.e., has had menses at any time in the preceding 24 consecutive months).

⁸ Pregnancy tests must occur within 10 – 14 days and again within 24 hours prior to prescribing lenalidomide (prescriptions must be filled within 7 days). FCBP with regular or no menstruation must have a pregnancy test weekly for the first 28 days and then every 28 days while on therapy (including breaks in therapy); at discontinuation of lenalidomide and at Day 28 post the last dose of lenalidomide. Females with irregular menstruation must have a pregnancy test weekly for the first 28 days and then every 14 days while on therapy (including breaks in therapy), at discontinuation of lenalidomide and at Day 14 and Day 28 post the last dose of lenalidomide (see Appendix I: Risks of Fetal Exposure, Pregnancy Testing Guidelines and Acceptable Birth Control Methods).

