5.6.2 Dosing Regimen

The trial will use a classical 3x3 phase I design for patients with GFR > 60ml/min and a modified 3x3 design for patients with GFR 30-59ml/min with enrollment of ten additional patients at the highest tolerated low dose (HTLD / HTLD-CKD) of azacitidine as outlined under 5.1. The dosing schedule is outlined below. Assigned combination treatment with lenalidomide, azacitidine, and dexamethasone will be continued for six 28-day cycles followed by maintenance treatment with lenalidomide single agent at the last tolerated dose until disease progression with adjustment of dose as outlined under 5.7.1 and 5.7.3.

Peripheral blood stem cell harvesting and high dose chemotherapy therapy may be performed at any point after treatment cycle #2. In such patients protocol therapy will be permanently discontinued at least five days before stem cell mobilization begins but in addition to the basic follow up outlined under 2, schedule of study assessments, their peripheral blood stem cell yield and engraftment will be documented.

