5.10 Follow-Up

Subjects who discontinue treatment for any reason, will be followed every 3 months for 3 years from study entry (if patients are no longer treated at this Institution attempts will be made to obtain information over the phone as per Schedule of Assessments, Section 2). Patients, who stay on protocol therapy will be followed at least every 2 months according to schedule of study assessments (2) for 3 years from study entry. At treatment discontinuation, off study evaluations per the Schedule of Assessments, Section 2, will be done. In addition, subjects will undergo a safety assessment approximately 28 days post the last dose of protocol therapy.

6 Adverse Events

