10.3 Statistical Methodology

The Kaplan-Meier method will be used to report progression free survival and overall survival for patients treated at the HTLD / HTLD-CKD and for the entire study cohort but excluding patients who elect to undergo high dose chemotherapy and autologous stem cell transplantation. For statistical methods pertaining to pharmacodynamic analyses please see under correlative science (5.5).

11 Regulatory Considerations

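### Leaving patients who elect autologous transplant out of the PFS and OS curves makes the analysis set depend on an event after study entry

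*Combined protocol and SAP*

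**What the plan says.** Three places in the analysis plan agree with one another:

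- Section 10.2.4 times PFS from enrollment to progression or death and says that patients who choose high-dose chemotherapy and "autologous stem cell transplantation will not be included in an analysis of progression-free survival".
- Section 10.2.5 times OS from study entry to death and says "Patients who elect to undergo high dose chemotherapy followed by autologous stem cell transplantation will not be included in an analysis of overall survival".
- Section 10.3 plans Kaplan-Meier curves for the HTLD / HTLD-CKD patients and for the whole cohort, in each case "excluding patients who elect to undergo high dose chemotherapy and autologous stem cell transplantation".

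This is exclusion, not censoring. No censoring rule for transplant and no sensitivity analysis is given. The endpoint definitions in section 4.2.2 do not mention the exclusion, though they do not contradict it.

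On timing, section 5.6.2 says "Peripheral blood stem cell harvesting and high dose chemotherapy therapy may be performed at any point after treatment cycle #2". It also says that stem cell yield and engraftment will be documented for these patients "in addition to the basic follow up outlined under 2, schedule of study assessments". Section 5.10 adds: "Subjects who discontinue treatment for any reason, will be followed every 3 months for 3 years from study entry".

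**The concern.** Whether a patient belongs to the analysis set is settled by something that happens at least 56 days after the clock starts. A patient who dies or progresses early and never reaches transplant always stays in. A patient who does well and goes to transplant is taken out, together with the event-free time already observed. The curve then describes a group that nobody could identify at entry.

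The direction is not fixed. Removing event-free patients of equal or better prognosis lowers the curve. The wording is not limited to transplant before progression, however, so a patient who progresses and is transplanted later is also dropped. That removes a PFS event and raises the curve. A reader of the report could not tell which effect dominates.

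The extension is meant to give a first impression of efficacy before a larger trial, and these curves contribute to it. The DLT endpoint, the response analysis and the sample size are not affected.

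**Working it through.** **The plan's own figures.** Synopsis: 18 patients started before amendment 7, 4 more to complete dose level 5, 12 with reduced GFR and 10 in the extension. 18 + 4 + 12 + 10 = 44, as stated. The HTLD / HTLD-CKD set is 6 + 10 = 16 to 6 + 6 + 10 = 22, matching section 10.2.3. The plan states no design figure for PFS or OS and no transplant rate, so the bias can only be sized under assumptions.

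**Inputs.** Section 3.3 cites a median time to progression of 11.1 months and a median OS of 29.6 months for lenalidomide with pulsed dexamethasone. They serve here only as a scale. Cycles last 28 days, so the ends of cycles 2, 4 and 6 fall at 1.84, 3.68 and 5.52 months (30.4375 days per month).

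**Assumptions.** Times are exponential. A fraction f of patients still event-free at time τ elects transplant, unrelated to prognosis.

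**Formula.** For t > τ the curve with these patients removed is S(t)(1 − f) / (1 − f·S(τ)). This is below S(t) for every f > 0. With true median m, the apparent median is m × log₂[2(1 − f) / (1 − f·S(τ))].

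Example: m = 11.1, τ = 3.68, f = 0.2. S(τ) = 2^(−3.68/11.1) = 0.795. Then 2 × 0.8 / (1 − 0.2 × 0.795) = 1.902, log₂ 1.902 = 0.928, and the apparent median is 10.3 months.

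| Transplant at end of | PFS median, f = 0.1 to 0.3 (true 11.1) | OS median, f = 0.1 to 0.3 (true 29.6) |
|---|---|---|
| cycle 2 | 10.91 to 10.37 | 29.40 to 28.84 |
| cycle 4 | 10.74 to 9.75 | 29.21 to 28.12 |
| cycle 6 | 10.59 to 9.21 | 29.03 to 27.44 |

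**By number of transplants.** Put f = k / (N·S(τ)) for k transplants among N patients, over the same three time points.

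| N | PFS median, k = 1 | PFS median, k = 3 |
|---|---|---|
| 16-22 | 11.01 to 10.65 | 10.79 to 9.50 |
| 44 | 11.05 to 10.95 | 10.96 to 10.61 |

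**Opposite direction.** Suppose a fraction g of patients progressing between 1.84 and 12 months is later transplanted and dropped. The share removed is g[S(1.84) − S(12)] = g(0.892 − 0.473). For g = 0.1 the share is 0.042 and the apparent median is 11.76 months. For g = 0.3 the share is 0.126 and the median is 13.25 months.

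**Sampling error for scale.** If all patients have events, the approximate 95% interval is 11.1 × exp(±1.96/√n): 6.8 to 18.1 months for n = 16 and 7.3 to 16.9 for n = 22.

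**Exclusion against censoring.** A simulation of 400,000 patients compared the two on 12-month PFS, with transplant leaving the hazard unchanged.

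| Election of transplant | Truth | Censored at transplant | Excluded |
|---|---|---|---|
| Unrelated to prognosis | 46.1% | 46.1% | 43.4% |
| Fitter patients elect it | 46.0% | 43.5% | 40.4% |

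**The case against.** The best defence is that transplant is not protocol therapy and the plan wants PFS unaffected by it; response before mobilization, CD34+ yield and engraftment are reported separately. That aim is legitimate for PFS, but exclusion does not achieve it, and the argument does not extend to OS.

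The effect may also be small. The endpoints are descriptive, with no hypothesis, threshold or decision attached. The synopsis describes treated patients with a median of 4.5 prior regimens and 88% refractory to lenalidomide, and section 10.2.3 allows for no transplants at all. The f = 0.3 rows are therefore arithmetic on an assumption, and the one-to-three-patient figures are the better guide. This stands and limits the weight of the point. Still, a confidence interval shows sampling error and does not show this bias.

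The upward scenario can be called strained, because sections 5.6.2 and 4.2.2 describe transplant as an exit from ongoing treatment. It is nevertheless within the literal wording. Section 5.6.2.4 lets some patients who progress on maintenance restart the combination, and section 5.6.2 sets no upper time limit on transplant. The 11.8 to 13.25 months show only that the direction is open.

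Finally, censoring is not a complete cure. When fitter patients elect transplant it leaves 2.5 of the 5.6 percentage points of bias (46.0 − 43.5 against 46.0 − 40.4). It remains closer to the truth than exclusion in both simulated settings.

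**Conclusion.** The concern holds. As written, the rule selects the PFS and OS analysis sets on a post-entry event, and the curves are biased if any patient is transplanted. With event-free transplants unrelated to prognosis and exponential times, one to three transplants among 16-22 patients move an 11.1-month median down to between 11.0 and 9.5 months. Patients transplanted after progression would move PFS the other way. The actual size cannot be known from the documents, is probably below sampling error, and is zero if nobody is transplanted. The case is clearest for OS, where all treated patients can be kept using follow-up already planned. This should be fixed, but it does not touch the primary objective.

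**What to change.** Rewrite sections 10.2.4, 10.2.5 and 10.3:

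- **OS:** include every treated patient from study entry to death, regardless of transplant.
- **PFS:** include every treated patient. Count any documented progression before transplant as an event. Censor patients transplanted before progression at the last response assessment before mobilization. A patient who left treatment without documented progression and is transplanted later is censored at the last response assessment available.
- **Reporting:** give the number and timing of transplants, and show transplant-excluded curves only as a sensitivity analysis.

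The cost is three paragraphs of wording and no new data. Survival is already collected after treatment (the section 2 schedule has a row "Obtain Follow-Up survival information"). For transplant before six cycles are complete, a footnote to that schedule says that the disease tests "should be repeated before mobilization begins for confirmation of their pre-transplant response"; section 4.2.2 also requires confirmation of response before mobilization. The follow-up column lists only survival and anti-cancer treatment, so PFS is censored at transplant rather than followed through it. Two downsides should be stated in the report: OS will include any effect of transplant, and PFS censoring is informative if election depends on prognosis.
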